	
The EOS Safety Follow-up Period will consist of 1 visit 1-week (\pm 3 days) following the Week 24 Visit or the ETV. In the event that the Week 24 Visit or the ETV occurs > 1 week following the last dose of the study drug, the EOS Safety Follow-up Visit may not be required. The ETV and/or EOS Safety Follow-Up Visit are not expected to be completed for subjects who withdraw full consent or are lost to follow up.
 
If necessary, the Investigator may decide to extend the follow-up visits beyond 1 week to monitor recovery of safety parameters (e.g., lymphopenia).

Planned Sample Size:	Approximately 400 subjects (~100 subjects per treatment arm)

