Efficacy Evaluation Criteria:	
Efficacy assessments include the PASI, the affected BSA, and the IGA. Health-related QoL assessments include the Quick Inventory of Depressive Symptomatology-Self Report (16 Items) (QIDS-SR16), the Dermatological Life Quality Index (DLQI), the 12-item Short Form Survey (SF-12), the Work Productivity and Activity Impairment Questionnaire: Psoriasis (WPAI:PSO), and evaluation of Health Economics and Outcomes Research (HEOR).
 
Other assessments (for subjects with psoriasis in the relevant areas) include the Nail Psoriasis Severity Index (NAPSI), the Psoriasis Scalp Score Index (PSSI), the Palmoplantar Psoriasis Physician's Global Assessment (PP PGA) score, and the Pruritus Numerical Rating scale (NRS). PD assessments would include immunological analysis of peripheral blood samples. Details of PD assessment will be provided in a separate protocol.

Pharmacokinetics Evaluation Criteria:	Not applicable
Safety Evaluation Criteria:	Adverse event (AE) incidence and severity, laboratory test results (hematology, clinical chemistry, urinalysis), vital signs (systolic and diastolic blood pressure, heart rate, respiratory rate), physical examination, ECGs, and pregnancy testing.

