7.3 Efficacy Assessments

Efficacy will be evaluated via psoriasis assessments and measures of QoL.

Psoriasis assessments include the PASI, the affected BSA, and the IGA. Subject-reported assessments of health-related QoL include the DLQI, 12-Item Short Form Survey (SF-12), the Quick Inventory of Depressive Symptomatology-Self Report (QIDS-SR), the WPAI:PSO, the HEOR, and the Pruritus NRS.

Other psoriasis assessments to be performed as applicable include the NAPSI for the target fingernail, the PSSI score, and the PP PGA score.

Brief descriptions of these assessments are presented as follows.

7.3.1 Co-Primary Efficacy Assessments: Psoriasis Area and Severity Index and Investigator's Global Assessment

The investigator or designee will assess the extent and severity of the subjects' psoriasis using the PASI scoring system and will perform a global assessment of disease severity using the IGA. The PASI scale is provided in [Appendix 1](#); the IGA is a 5-point scale which measures the investigator's or designee's impression of the disease at a single point. Assessments will be performed at the visits specified in [Table 1-1](#). Sites should make every effort to ensure consistency in evaluators across visits, especially between Baseline and Week 24.

Psoriasis Area and Severity Index

The PASI is a measure of the average redness, thickness, and scaliness of the lesions (each graded on a 0–4 scale) and weighted by the area of involvement ([Fredriksson, 1978](#)). There are a few validation studies performed describing, with some limitations, the construct validity, face validity, and sensitivity to change ([Ashcroft, 1999](#)). National Psoriasis Foundation Medical Advisory Board standardized the definitions of events of psoriasis recurrence based on PASI, including the definition of relapse, which is a loss of at least 50% of PASI improvement after discontinuation of treatment in patients who had achieved a clinically meaningful response; and rebound, which is PASI \geq 125% of Baseline or new generalized pustular, erythrodermic, or more inflammatory psoriasis ([Carey, 2006](#); [Gordon, 2005](#)). In the current trial, PASI improvement will be evaluated from Baseline to all visits during the Titration and Treatment Periods, and clinically meaningful response is defined as PASI-50 ([Carlin, 2004](#)).

Investigator's Global Assessment

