7.5.5 Vital Signs

Measurements of vital signs, including blood pressure, pulse rate, and respiratory rate, will be taken at every visit with the subject seated.

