8.8.3 Vital Signs

Change in vital sign data will be classified as normal, low, high, based on a reference range. Observed and changes in vital sign parameters will be analyzed descriptively by time of collection and treatment group. Subjects with markedly abnormal changes will be listed and tabulated separately.

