## 9. HANDLING OF MISSING DATA

All imputations specified in this section will be performed for the Double-Blind Treatment and titration Period only; the Post-treatment Follow-Up Period data will be analyzed as observed.

For the analyses of the co-primary endpoints (PASI-75 and IGA), multiple imputation (MI) will be the primary imputation method. The modified non-responder imputation (m-NRI) and last observation carried (LOCF) method will be used as sensitivity analyses.

Details of the imputation methods are as following:

- **MI:** Missing data will be imputed using multiple imputations, a simulation-based approach where missing values are replaced by multiple Bayesian draws from the conditional distribution of missing data given the observed data and covariates, creating multiple completed data sets. These completed datasets can then be analyzed using standard analysis methods. MI will be implemented for all subjects with missing data, included those who used rescue medications or discontinued due to unsatisfactory therapeutic effect.

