Median	XX	XX	XX	XX
Minimum, Maximum	XX, XX	XX, XX	XX, XX	XX, XX
Change from baseline				
N	XX	XX	XX	XX
Mean (SD)	XX.X (XX.X)	XX.X (XX.X)	XX.X (XX.X)	XX.X (XX.X)
Median	XX	XX	XX	XX
Minimum, Maximum	XX, XX	XX, XX	XX, XX	XX, XX

Note: PASI-50 responder is defined as achieving a reduction of 50% or greater from baseline. Baseline is the last available measurement prior to the first dose of study drug on Day 1.

Generated on XX/XX/XX:XXXX by XXX / Uses: XXXX / Reference: Listing XXXX

<Repeat for>

Table 14.3.2.3.2: Lymphocyte Counts by Clinical Response of PASI-75 at Week 24  
Safety Population

---

Note: PASI-75 responder is defined as achieving a reduction of 75% or greater from baseline. Baseline is the last available measurement prior to the first dose of study drug on Day 1.

Table 14.3.2.4.1: Clinical Laboratory Results, Shifts from Baseline by Visit  
Chemistry  
Safety Population  
[Lab Tests Name (Units)]

	PPC-06 400 mg QD (N=XX)	PPC-06 400 mg BID (N=XX)	PPC-06 600 mg BID (N=XX)	Placebo (N=XX)
Baseline -> Week 4, n (%)				
N [1]	XX	XX	XX	XX
Low -> Normal	XX (XX.X)	XX (XX.X)	XX (XX.X)	XX (XX.X)
Normal -> Normal	XX (XX.X)	XX (XX.X)	XX (XX.X)	XX (XX.X)
High -> Normal	XX (XX.X)	XX (XX.X)	XX (XX.X)	XX (XX.X)
<Include all possible shifts as rows>				
Baseline -> Week 8, n (%)				
N [1]	XX	XX	XX	XX
Low -> Normal	XX (XX.X)	XX (XX.X)	XX (XX.X)	XX (XX.X)
Normal -> Normal	XX (XX.X)	XX (XX.X)	XX (XX.X)	XX (XX.X)
High -> Normal	XX (XX.X)	XX (XX.X)	XX (XX.X)	XX (XX.X)
<Include all possible shifts as rows>				
Baseline -> Week 12, n (%)				
N [1]	XX	XX	XX	XX
Low -> Normal	XX (XX.X)	XX (XX.X)	XX (XX.X)	XX (XX.X)
Normal -> Normal	XX (XX.X)	XX (XX.X)	XX (XX.X)	XX (XX.X)
High -> Normal	XX (XX.X)	XX (XX.X)	XX (XX.X)	XX (XX.X)
<Include all possible shifts as rows>				

<continue with: Week 16, Week 20, Week 24>

[1] # of subjects with both baseline and post-baseline visits, this is the denominator for calculating the percentage.

Generated on XX/XX/XX:XXXX by XXXXX / Uses: XXXX / Reference: Data Listings XXXX

*<Repeat table for>*

Table 14.3.2.4.2: Clinical Laboratory Results, Shifts from Baseline by Visit  
Hematology  
Safety Population  
[Lab Tests Name (Units)]

Table 14.3.3.1: Summary of Vital Signs by Treatment and Visit  
Safety Population  
[Pulse Rate (bpm)][ Systolic Blood Pressure (mmHg)][ Diastolic Blood Pressure (mmHg)]

	PPC-06 400 mg QD (N=XX)	PPC-06 400 mg BID (N=XX)	PPC-06 600 mg BID (N=XX)	Placebo (N=XX)

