Baseline				
Observed Values				
N	XX	XX	XX	XX
Mean (SD)	XX.X (XX.X)	XX.X (XX.X)	XX.X (XX.X)	XX.X (XX.X)
Median	XX	XX	XX	XX
Minimum, Maximum	XX, XX	XX, XX	XX, XX	XX, XX
Week 4				
Observed Values				
N	XX	XX	XX	XX
Mean (SD)	XX.X (XX.X)	XX.X (XX.X)	XX.X (XX.X)	XX.X (XX.X)
Median	XX	XX	XX	XX
Minimum, Maximum	XX, XX	XX, XX	XX, XX	XX, XX
Change from Baseline				
N	XX	XX	XX	XX
Mean (SD)	XX.X (XX.X)	XX.X (XX.X)	XX.X (XX.X)	XX.X (XX.X)
Median	XX	XX	XX	XX
Minimum, Maximum	XX, XX	XX, XX	XX, XX	XX, XX

<Repeat for Week 8, Week 12, Week 16, Week 20, Week 24>

Note: Baseline is the last available measurement prior to the first dose of study drug on Day 1.

Generated on XX/XX/XX:XXXX by XXX / Uses: XXXX / Reference: Listing XXXX

Table 14.3.3.2: Summary of Vital Signs, Shifts from Baseline by Visit  
Safety Population  
[Pulse Rate (bpm)][ Systolic Blood Pressure (mmHg)][ Diastolic Blood Pressure (mmHg)]

	PPC-06 400 mg QD (N=XX)	PPC-06 400 mg BID (N=XX)	PPC-06 600 mg BID (N=XX)	Placebo (N=XX)
Baseline -> Week 4, n (%)				
N [1]	XX	XX	XX	XX
Low -> Normal	XX (XX.X)	XX (XX.X)	XX (XX.X)	XX (XX.X)
Normal -> Normal	XX (XX.X)	XX (XX.X)	XX (XX.X)	XX (XX.X)
High -> Normal	XX (XX.X)	XX (XX.X)	XX (XX.X)	XX (XX.X)
<Include all possible shifts as rows>				
Abnormal Change from Baseline	XX (XX.X)	XX (XX.X)	XX (XX.X)	XX (XX.X)
Markedly Abnormal Change from Baseline	XX (XX.X)	XX (XX.X)	XX (XX.X)	XX (XX.X)
Baseline -> Week 8, n (%)				
N [1]	XX	XX	XX	XX
Low -> Normal	XX (XX.X)	XX (XX.X)	XX (XX.X)	XX (XX.X)
Normal -> Normal	XX (XX.X)	XX (XX.X)	XX (XX.X)	XX (XX.X)
High -> Normal	XX (XX.X)	XX (XX.X)	XX (XX.X)	XX (XX.X)
<Include all possible shifts as rows>				
Abnormal Change from Baseline	XX (XX.X)	XX (XX.X)	XX (XX.X)	XX (XX.X)
Markedly Abnormal Change from Baseline	XX (XX.X)	XX (XX.X)	XX (XX.X)	XX (XX.X)

<continue with other visits: Week 12, Week 16, Week 20, Week 24>

Note: Pulse Rate: Low=<50bpm; Normal=50-100bpm; High=>100bpm; Abnormal change from baseline: >=10bpm; Markedly abnormal change from baseline: >=30bpm.

Systolic Blood Pressure: Low= <90mmHg; Normal= 90-140mmHg; High= >140mmHg; Abnormal change from baseline: >=20mmHg; Markedly abnormal change from baseline: >=40mmHg. Diastolic Blood Pressure: Low= <50mmHg; Normal= 50-90mmHg; High= >90mmHg; Abnormal change from baseline: >=10mmHg; Markedly abnormal change from baseline: >=20mmHg.

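### Respiratory rate has no planned output, post-baseline weight has no by-arm summary, and the Visit 9 window files ordinary Week 25 off-drug values under Week 24

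*Protocol*

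**What the plan says.** **Respiratory rate.** The Protocol Synopsis lists among the safety evaluation criteria "vital signs (systolic and diastolic blood pressure, heart rate, respiratory rate), physical examination, ECGs, and pregnancy testing". Protocol 7.5.5 adds: "Measurements of vital signs, including blood pressure, pulse rate, and respiratory rate, will be taken at every visit with the subject seated". Protocol 8.8.3 commits to an analysis: "Observed and changes in vital sign parameters will be analyzed descriptively by time of collection and treatment group". SAP 12.9.3 repeats that commitment by visit and treatment group, but its table of reference ranges covers only systolic pressure, diastolic pressure and pulse. The shells for Tables 14.3.3.1 and 14.3.3.2 are headed "Pulse Rate (bpm)][ Systolic Blood Pressure (mmHg)][ Diastolic Blood Pressure (mmHg". Listing 16.2.8.4 has columns for weight, the two pressures and pulse, and none for respiratory rate. SAP 13 records one change from the protocol, which concerns PP PGA.

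**Weight.** Protocol Table 1-1 places weight under Safety Assessments at Screening, at Weeks 4 to 24 and at the early termination visit (ETV). Protocol 8.4 promises weight as a demographic, and Table 14.1.2.X gives it by arm at baseline. After baseline it appears only in Listing 16.2.8.4, without the change-from-baseline column that blood pressure and pulse have.

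**Follow-up.** The Synopsis says "The EOS Safety Follow-up Period will consist of 1 visit 1-week" after Week 24 or the ETV. Vital signs, ECG, PASI, BSA and IGA are all collected there (Table 1-1, Protocol 7.2.5). SAP 9 says "the Post-treatment Follow-Up Period data will be analyzed as observed", and SAP 11.4 says Visit 9 will be analysed by days since last dose. The instruction under Table 14.3.3.1 is "<Repeat for Week 8, Week 12, Week 16, Week 20, Week 24>". Tables 14.3.3.2 and 14.3.4 and the by-visit efficacy shells likewise do not go past Week 24. SAP 11.4 sets the Visit 9 target at last dose (LD) + 7 and its window at more than LD + 15.

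**The concern.** Safety and tolerability is a stated secondary objective. If the SAP shells are programmed as written, one vital sign that the protocol names will produce no output at all. Protocol 8.10 lets the SAP prevail where the two differ, so the gap would not correct itself.

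The follow-up visit is one of the four study periods and the only planned off-drug observation. Two things go wrong with it. No vital-sign, ECG or efficacy table has a row for it, although the SAP says its data will be analysed. And the visit window sends most of its records to on-treatment visits, so off-drug values can enter results labelled as on-treatment, including Week 24, the time point of the co-primary endpoints.

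Weight is a lesser matter. Protocol 7.5.1.4 names diarrhea, nausea and abdominal pain as common effects of the drug. Weight is a simple objective measure that bears on them and is already being collected.

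**Working it through.** The plan states no figure on this point, so the check is a trace from collection to output, followed by a count under the SAP 11.4 window rules.

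**Step 1. Trace each item.**

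| Item | Collected | Analysis stated | Table by arm | Listing |
|---|---|---|---|---|
| Respiratory rate | Visits 1 to 9 | Protocol 8.8.3, SAP 12.9.3 | None | None |
| Weight after baseline | Weeks 4 to 24, ETV | None | None | 16.2.8.4, value only |
| Week 25 blood pressure, pulse | Yes | Protocol 8.8.3, SAP 11.4 | No row after Week 24 | 16.2.8.4 |
| Week 25 ECG | Yes | Protocol 8.8.4, SAP 12.9.5 and 11.4 | No row after Week 24 | 16.2.8.6.1 |
| Week 25 PASI, IGA | Yes | SAP 9 and 11.4 only | No row after Week 24 | 16.2.6.1.1, 16.2.6.1.2, 16.2.6.2 |

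**Step 2. Which Week 25 records become Visit 9?** Let g be days from last dose to the Week 24 visit, and f be days from Week 24 to the follow-up visit. A record becomes Visit 9 only if g + f > 15.

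- The follow-up visit may be omitted when Week 24 is more than 1 week after last dose, so g runs from 0 to 7.
- Table 1-1 and Protocol 7.2.5 allow +3 days, so f runs from 7 to 10. This gives 8 × 4 = 32 combinations, of which 3 exceed 15: (6,10), (7,9) and (7,10).
- The Synopsis and SAP 3 allow ±3 days, so f runs from 4 to 10. This gives 8 × 7 = 56 combinations, with the same 3 exceeding 15.
- Protocol 4.1 waives the visit at 1 week or more, so g runs from 0 to 6. With f from 7 to 10 this gives 7 × 4 = 28 combinations, of which 1 exceeds 15.

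These are counts of day pairs, not probabilities. A subject whose last dose is on the day of the Week 24 visit and who returns 7 to 10 days later is at LD + 7 to LD + 10. That is on target by the SAP's own table, yet it is assigned to the Week 24 window (Day 155 onward).

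**Step 3. When would that record be used as Week 24?** SAP 11.4 takes the record closest to Day 168, and the later one in a tie. Take a Week 24 visit on Days 165 to 171.

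- With f from 7 to 10, the follow-up record is never as close as the Week 24 visit, so it is used only if the Week 24 value is missing.
- With f from 4 to 10, it is as close or closer in 4 of 7 × 7 = 49 pairs: Days (165,169), (165,170), (165,171) and (166,170). It would then displace an actual Week 24 value.

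**Step 4. LOCF.** SAP 11.4 uses the later visit within a window for LOCF. As an illustration, let last dose be Day 84, the ETV Day 86 and follow-up Day 93. Then 93 − 84 = 9, which is within 15, and Day 93 lies in the Week 12 window (Days 71 to 98). The off-drug Day 93 value is the one carried forward to Week 24.

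**Step 5. What a weight table could show.** The documents give no SD for weight change. Assume 4 kg, with a range of 3 to 6. For one dose against placebo at one visit, SE = SD × √(2/n).

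- SD 4: 0.57 kg at n = 100 and 0.80 kg at n = 50 per arm. Multiplying by 1.96 gives 1.11 and 1.57 kg.
- SD 3 at n = 100 gives SE 0.42 kg; SD 6 at n = 50 gives 1.20 kg.

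**The case against.** Much of the opposing case is right, and it limits the point.

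- **Weight.** It is not in the protocol's list of vital signs or its safety endpoints. Protocol 8.4 promises it only as a demographic, which the SAP delivers. A weight-change table is a recommendation, and SAP 13 had nothing to declare. The 4 kg SD is an assumption, and the 1.1 to 1.6 kg range allows for neither three doses nor six visits.
- **Rebound.** A reader might infer that a promised count of relapse or rebound was dropped, since Protocol 7.3.1 describes "relapse, which is a loss of at least 50% of PASI improvement after discontinuation of treatment". That text reports an outside board's definitions. The same paragraph limits PASI evaluation in this trial to the Titration and Treatment Periods, and the by-visit endpoints are limited to the Double-Blind Treatment Period. Any commitment to analyse Week 25 efficacy comes only from the general wording of SAP 9 and 11.4.
- **Nothing from Week 25 is usable.** A reader might also infer that every Week 25 value is lost, or that the arms cannot be compared. Apart from respiratory rate, the variables are in by-subject listings paged by arm. Adverse events are collected at Week 25 and tabulated by arm, and weight loss could be reported as one. Step 2 shows that most Week 25 records are reassigned to the Week 24 window and not discarded.
- **Follow-up rows would be nearly empty.** This is correct while the Visit 9 window stands. The few records would come mainly from subjects who returned late. The window therefore has to be settled first.
- **Numbers.** The follow-up set will be well short of 400. The plan assumes 50% dropout, the visit can be waived, and it is not expected after full withdrawal of consent or loss to follow-up.

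None of this answers the missing respiratory rate, the SAP statements about follow-up analysis with no table behind them, or the conflict between the Visit 9 window and its target.

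**Conclusion.** The point holds in three parts of unequal weight.

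1. **Respiratory rate** is an undeclared departure from an explicit commitment: nine scheduled measurements per completing subject, and no table or listing. This rests on the text alone.
2. **Follow-up data** are said to be analysed but have no vital-sign, ECG or efficacy table row. The Visit 9 definition contradicts its own target day and captures 1 of 28 to 3 of 32 day combinations (3 of 56 on the ±3-day reading). Ordinary follow-up records become Week 24 candidates. They are used when Week 24 is missing, through the LOCF rule, or, on the ±3-day reading, in 4 of 49 pairings even when Week 24 is present. How often this would happen depends on actual visit timing, which the documents cannot show.
3. **Post-baseline weight** lacks a by-arm summary. This is a worthwhile addition, not a broken promise.

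The documents do not support saying that off-drug or weight comparisons are impossible, or that a rebound analysis was planned and omitted. The gap is in planned summaries and in how records are classified, not in data collection.

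**What to change.** 1. Add respiratory rate to Table 14.3.3.1 and Listing 16.2.8.4. If it is not to be summarised, declare that in SAP 13 with a reason.
2. Add weight to Table 14.3.3.1 as change and percent change from baseline, and add a change column in Listing 16.2.8.4. Table 1-1 shows no weight at the Baseline visit, whereas Protocol 7.5.6 reads as if there is one. State that baseline follows SAP 11.3 (last value before first dose).
3. Reconcile the Visit 9 window in SAP 11.4 with its LD + 7 target so that Week 25 records are classed as follow-up and cannot enter Week 24 or LOCF. State how ETV records are handled under the revised rule. Align the +3 and ±3 day statements and the two wordings of the 1-week waiver.
4. After that, add observed-case follow-up rows to Tables 14.3.3.1, 14.3.3.2 and 14.3.4.
5. Optionally, add one descriptive table of Week 25 PASI by arm with days since last dose. A relapse or rebound count would go beyond the protocol and should be labelled as such.

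The cost is a few shell rows, one listing column each for respiratory rate and weight change, and one revised window rule, settled before unblinding. No new data are needed. The window change alters which records feed Week 24 and LOCF, so it belongs in a dated SAP amendment.

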2. INTRODUCTION

The investigational product (IP) in this study is PPC-06 (tepilamide fumarate) extended release (ER) tablets, previously known as XP23829, which is a patented, oral product candidate that utilizes prodrug technology for efficient absorption into the body. Once absorbed, PPC-06 is rapidly converted to monomethyl fumarate (MMF), a fumaric acid ester (FAE) compound that has shown immunomodulatory and neuroprotective effects in cell-based systems and various preclinical models of disease. The current trial will examine the safety and efficacy of PPC-06 in the treatment of moderate-to-severe plaque-type psoriasis.

2.1 Plaque Psoriasis

Psoriasis is a chronic T-cell-mediated autoimmune disease ([Ghoreschi, 2007](#)) that affects 2% to 3% of the US population ([Stern, 2004](#); [Kurd, 2009](#)) and 0.6% to 6.5% of the European population ([Chandran, 2010](#)). As many as an estimated 7.5 million Americans are thought to have psoriasis, making it the most common autoimmune disease in the United States ([National Psoriasis Foundation](#)). The most common phenotypic form of psoriasis, plaque psoriasis, manifests as raised, well-demarcated, red plaques with silver scales that may remit spontaneously or recur in response to environmental triggers ([Nestle, 2009](#)).

In addition to the appearance of skin plaques, there is a high degree of physical morbidity associated with psoriasis. Up to 30% of patients develop psoriatic arthritis ([Zanni, 2012](#)). Individuals with psoriasis appear to be at higher risk for a number of co-morbid conditions including obesity, myocardial infarction, cancer, diabetes mellitus, Crohn's disease and depression ([Krueger, 2001](#); [Davidovici, 2010](#); [Mehta, 2010](#)). Patients with severe psoriasis, on average, die five years younger than patients without psoriasis, an observation that is largely attributable to an increased risk of cardiovascular disease ([Prodanovich, 2009](#)). In addition, psoriasis can represent both a significant social and financial burden for patients. Individuals suffer from both disfigurement and social stigmatization, with an impact on mental disability comparable with that of other major medical illnesses such as heart disease and rheumatoid arthritis ([Sterry, 2009](#)). Patients with psoriasis, like those with other major medical disorders, have a reduced quality of life (QoL) and reduced levels of employment and income ([Horn, 2007](#)).

The currently available psoriasis treatments do not offer a cure. Treatment is aimed at reducing the burden of disease and achieving an improvement in its signs and symptoms ([Laws, 2012](#)). Topical agents are generally prescribed for mild and some moderate cases, while systemic agents (including biologics), and phototherapy are reserved for moderate and severe cases. Treatment decisions are based not only on the severity of the disease, but also on existing comorbidities, tolerability, side effects, and patient preferences. Several systemic agents, including methotrexate (MTX), cyclosporine, and retinoids are most commonly used ([Laws, 2012](#)). Various factors limit favorable long-term outcomes; in particular, a lack of consistent efficacy over time and the risk

of serious cumulative toxicity. Injectable biologic agents are effective for a substantial number of patients, but there is concern regarding long-term safety due to the risk of immunosuppression and the potential for development of infections, opportunistic diseases, or malignancy ([Laws, 2012](#); [Palfreeman, 2013](#)).

